5.1.4. Visit 4 (Day 15 ± 2 Days) – 1st Follow-up

The following assessments should be evaluated at this visit:

- (1) Conduct physical exam
- (2) Measure vital signs
- (3) Collect NIAID 8-point ordinal scale
- (4) Assess pulse oxygen saturation: measure SpO₂ and record FiO₂
- (5) Perform 12-lead ECG
- (6) Perform chest X-ray
- (7) Collect urine and blood samples for the following laboratory tests.
 - Hematology
 - Blood Chemistry
 - Coagulation
 - Urinalysis
 - Biomarker evaluations
- (8) Provide SOC/supportive care (as needed)
- (9) Check ePRO completion status
- (10) Record hospitalization events and ER visit, if any
- (11) Record any change of concomitant medication
- (12) Record adverse events and check mortality status, if needed

5.1.5. Visit 5 (Day 29 ± 3 Days) – 2nd Follow-up, the end of study (EOS)/early termination (ET)

The following assessments should be evaluated at this visit:

- (1) Conduct physical exam
- (2) Measure vital signs
- (3) Collect NIAID 8-point ordinal scale
- (4) Assess pulse oxygen saturation: measure SpO₂ and record FiO₂
- (5) Perform 12-lead ECG
- (6) Perform chest X-ray
- (7) Collect urine and blood samples for the following laboratory tests.
 - Hematology
 - Blood Chemistry
 - Coagulation
 - Urinalysis
 - Biomarker evaluations
- (8) Perform pregnancy test: Only for female with child bearing potential when early termination occurs before the completion of Visit 3
- (9) Collect nasopharyngeal swab samples for RT-PCR (only performed when early termination occurs before the completion of Visit 3)
- (10) Provide SOC/supportive care (as needed)
- (11) Check ePRO completion status (as needed)
- (12) Record hospitalization events and ER visit, if any
- (13) Record any change of concomitant medication
- (14) Record adverse events and check mortality status, if needed

5.2. Study Assessments

5.2.1. Eligibility and informed consent

Subjects will be screened prior to the start of the study treatment. All assessments will be performed after the subjects have signed and dated the informed consent form.

The investigator or a designee will explain the nature of the study to subjects. The subject will be given an informed consent form to be read carefully before agreeing to take part in the study and before the study-specific procedures take place. The informed consent form should be reviewed, signed, and dated by the subject and the investigator. A copy of the statement will be given to the subject, and the

original should be maintained by the investigator in the site master file. After informed consent being obtained, designed procedures and assessments will be initiated to determine eligibility.

5.2.2. Demographic data, medical history, and concomitant medication

Demographic data will be collected at the screening visit. Demographic data includes birth year, age, and sex.

Any pre-treatment medical events will be recorded as medical history. The general medical history within 2 weeks before Screening Visit should be recorded at Screening Visit. The general medical history includes chronic diseases, allergic history, surgical history, and disease of interests, such as pulmonary, gastrointestinal, cardiovascular, cerebrovascular, and autoimmune events, cystic fibrosis, dementia, and acute or chronic infection. History of severe renal disease and documented anaphylactic reaction should be recorded in a lifetime basis.

Concomitant medication will be recorded when subjects received the following:

- Medication from 2 weeks prior to screening visit to end of the study
- Any investigational treatment within 30 days prior to the study
- SARS-CoV-2 specific monoclonal antibody or convalescent COVID-19 plasma treatment prior to screening

5.2.3. Pneumonia severity index

For each subject, the risk class of Pneumonia Severity Index (PSI) will be recorded. PSI is a clinical prediction rule which can be used to calculate the probability of morbidity and mortality for community acquired pneumonia. It is used to predict the need for hospitalization in people with pneumonia.

Table 5-1 PSI Algorithm

Step 1: Stratify to Risk Class I vs. Risk Classes II-V	
Presence of:	
Over 50 years of age	Yes/No
Altered mental status	Yes/No
Pulse \geq 125/minute	Yes/No
Respiratory rate $>$ 30/minute	Yes/No
Systolic blood pressure $<$ 90 mm Hg	Yes/No
Temperature $<$ 35 °C or \geq 40 °C	Yes/No

Step 1: Stratify to Risk Class I vs. Risk Classes II-V	
History of:	
Neoplastic disease	Yes/No
Congestive heart failure	Yes/No
Cerebrovascular disease	Yes/No
Renal disease	Yes/No
Liver disease	Yes/No
If any "Yes", then proceed to Step 2	
If all "No" then assign to Risk Class I	

Step 2: Stratify to Risk Class II vs III vs IV vs V	
Demographics	Points Assigned
If Male	+Age (yr)
If Female	+Age (yr) - 10
Nursing home resident	+10
Comorbidity	
Neoplastic disease	+30
Liver disease	+20
Congestive heart failure	+10
Cerebrovascular disease	+10
Renal disease	+10
Physical Exam Findings	
Altered mental status	+20
Pulse \geq 125/minute	+10
Respiratory rate $>$ 30/minute	+20
Systolic blood pressure $<$ 90 mm Hg	+20
Temperature $<$ 35 °C or \geq 40 °C	+15
Lab and Radiographic Findings	
Arterial pH $<$ 7.35	+30
Blood urea nitrogen \geq 30 mg/dl (9 mmol/liter)	+20
Sodium $<$ 130 mmol/liter	+20
Glucose \geq 250 mg/dl (14 mmol/liter)	+10
Hematocrit $<$ 30%	+10

Step 2: Stratify to Risk Class II vs III vs IV vs V	
Partial pressure of arterial O ₂ <60mmHg	+10
Pleural effusion	+10
$\Sigma < 70 = \text{Risk Class II}$	
$\Sigma 71-90 = \text{Risk Class III}$	
$\Sigma 91-130 = \text{Risk Class IV}$	
$\Sigma > 130 = \text{Risk Class V}$	

A pneumonia severity index will be assessed at screening visit.

5.2.4. Efficacy Assessments

5.2.4.1. Hospitalization and Emergency Room Visit

If a participant is hospitalized or during emergency room (ER) visit, procedures and assessments will continue per the visit schedule. Hospitalization is defined as inpatient admission and more details are listed in **Section 5.2.5.6.** Hospitalization event will be followed up until Day 29.

This table describes discharge from hospital scenarios if an outpatient is subsequently hospitalized.

Table 5-2 Discharge from hospital (Outpatients Subsequently Hospitalized)

If hospital discharge...	Then....
Occurs prior to Day 29	Subjects will be asked to complete the remaining study assessments at the time points indicated in the visit schedule.
Occurs on the same day as a scheduled study visit	
If the scheduled study assessments are performed during hospitalization and the circumstances meet all the following criteria, assessments do not need to be repeated.
 
• The scheduled study assessments have been performed within 8 hours of discharge.• There has been no change in clinical status.• The information is available to the site.

5.2.4.2. Chest X-ray

Chest X-ray will be performed at Visits 1, 3, 4, and 5. The results obtained at Visit 1 should be baseline before the start of treatment. The findings will be evaluated by the investigators and noted as “Normal”, “Abnormal, non-clinical significant (NCS)” or “Abnormal, clinical significant (CS)” with comments in the CRF/eCRF. Any clinical significant abnormal findings should be recorded as an adverse event during the study. Post-treatment pneumonia status, as assessed by the chest X-ray, will be categorized as ‘Worsen’, ‘No Change’, ‘Improved’ or ‘Normal’.

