3.2.2. Inclusion criteria

Subjects meeting all of the following criteria will be considered for enrollment into the study:

1. Not currently hospitalized
2. Males or females aged ≥ 18 years at the time of signing the informed consent form (ICF)
3. Patients diagnosed with viral pneumonia, as determined by the investigator, who exhibit any of the subsequent criteria: presence of respiratory symptoms or fever (ear temperature ≥ 38 °C, base of the tongue temperature ≥ 37.5 °C, or axillary temperature ≥ 37 °C)
4. With a pneumonia severity index (PSI) of risk class II or III
5. Oxygen saturation measured by pulse oximetry (SpO_2) $\geq 94\%$ on room air at sea level
6. Positive test for SARS-CoV-2 or influenza virus infection, confirmed by rapid diagnostic test (excluding cases where both SARS-CoV-2 and influenza virus are positive)
7. Confirmed lower respiratory tract infection by X-ray
8. At screening, subjects capable of childbearing must provide a negative serum or urine pregnancy test. These subjects must also commit to adhering to the study-specified contraceptive methods throughout the study duration

Notes: Acceptable contraceptive methods include:

- Established use of oral, injected or implanted hormonal methods of contraception
- Placement of an intrauterine device (IUD) or intrauterine system (IUS)
- Barrier methods of contraception: condom or occlusive cap (diaphragm or cervical/vault caps)

9. The participant (or legal representative) agrees and is able to adhere to study protocol-stated requirements, instructions, and restrictions in the investigator's judgement. Furthermore, the participant is capable of understanding and has signed the IRB-approved Informed Consent Form (ICF)

10. With at least two of the risk factors listed below:

Age \geq 50 years-old; cancer and a life expectancy of \geq 6 months; HIV infection; immunocompromised patient; congestive heart failure (CHF), or coronary artery disease (CAD), or cardiomyopathies; chronic kidney disease (CKD); chronic liver disease; chronic lung disease; diabetes mellitus (DM); body mass index (BMI) $> 25 \text{ kg/m}^2$; asthma; cerebrovascular disease; cystic fibrosis; dementia; or current and former smoker

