6.1. Adverse Event (AE)

An adverse event (AE) can therefore be any unfavorable and unintended sign (including an abnormal laboratory finding, for example), symptom, or disease temporally associated with the use of a medicinal product, whether or not considered related to the study medication. (Definition per International Conference on Harmonization [ICH]). A medical occurrence fulfills the definition of SAE in section 6.2 is also an AE.

Except for SAEs, Adverse Events are NOT:

- Clinical events related to expected progression of COVID-19 or influenza.
- Medical or surgical procedures (e.g., surgery, endoscopy, tooth extraction, transfusion). However, the condition that leads to the procedure is an AE.
- Situations where an untoward medical occurrence has not occurred (e.g., hospitalization for elective surgery, social and/or convenience admissions).

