6.1.1. Treatment Emergent Adverse Event (TEAE)

A treatment-emergent adverse event (TEAE) is defined as any unfavorable and unintended disease or its sign (including an abnormal laboratory value) in a subject who received the study drug, irrespective of the causal relationship with the study drug.

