6.5. Reporting Procedure

6.5.1. Adverse Event (AE)

Any AE occurring from the time the subject takes the first dose of the IP will be collected as treatment-emergent adverse events (TEAE) and the safety analysis will be carried out with TEAE. All TEAEs, regardless of seriousness, severity, or presumed relationship to study regimen, will be evaluated and recorded by investigators preferably with a diagnosis or medical terminology instead of signs, symptoms, and/or other clinical information on the TEAE form of CRF until recoverable or stable without a further follow-up by investigators' opinions. All measures required for adverse event management must be recorded in the source document and reported according to sponsor instructions.

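### The chest X-ray rule for adverse events has no new-or-worse condition, so the overall TEAE rate may include the pneumonia that qualified subjects for the trial

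*Protocol*

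**What the plan says.** - **Protocol 5.2.4.2, schedule and AE rule.** "Chest X-ray will be performed at Visits 1, 3, 4, and 5". Visit 1 is the baseline, so each subject has three later films. The investigator grades a film normal, abnormal but not clinically significant (NCS), or abnormal and clinically significant (CS). Then: "Any clinical significant abnormal findings should be recorded as an adverse event during the study".
- **Protocol 5.2.4.2, change from baseline.** "Post-treatment pneumonia status, as assessed by the chest X-ray, will be categorized as" Worsen, No Change, Improved or Normal. The AE sentence does not use this second grading.
- **Protocol 3.2.2, inclusion criterion 7.** "Confirmed lower respiratory tract infection by X-ray".
- **Protocol 6.1.** A list opens with "Except for SAEs, Adverse Events are NOT", and its first item is "Clinical events related to expected progression of COVID-19 or influenza".
- **Protocol 6.1.1.** A TEAE is "any unfavorable and unintended disease or its sign (including an abnormal laboratory value) in a subject who received the study drug", whatever the cause. There is no worsening criterion.
- **Protocol 6 and 6.5.1.** Medical events before treatment go to medical history, and "Any AE occurring from the time the subject takes the first dose of the IP will be collected as treatment-emergent adverse events".
- **SAP 3.2.5.** All reported AEs are summarized in an overview and by system organ class and preferred term. Events of the disease under study are not separated.
- **SAP 3.2.4.** The same films supply the secondary endpoint on X-ray improvement or return to normal.

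**The concern.** Safety and tolerability is a stated secondary objective, and the TEAE rate is its main summary. In a pneumonia trial an abnormal film after baseline is often just the entry disease. A recording rule that does not compare with the baseline film can turn that disease into a treatment-emergent event.

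Two sites could handle the same film differently and each point to a section of the protocol in support. The any-TEAE rate would then mix drug effects, the qualifying pneumonia and site habit. The films also measure efficacy, so a difference in X-ray clearance between arms could appear as a difference in safety.

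**Working it through.** The plan states no figure on this point, so there is none to reproduce. The check is mainly one of text.

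**Step 1. Set the rules side by side** for a film graded CS at Visit 3, 4 or 5.

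| Film | 5.2.4.2 | 6.1 | Medical-history and first-dose rules |
|---|---|---|---|
| Infiltrate persists or is improving | AE, read literally | Silent: this is not progression | May lead a site to omit it; not stated |
| Worse, non-serious, attributed to expected progression | AE | Not an AE | Do not settle it: the worsening follows dosing |
| Worse, and an SAE | AE | AE, through the SAE exception | No conflict |
| New finding unrelated to the qualifying pneumonia | AE | AE | No conflict |

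The first row is a gap and the second a contradiction. Sections 5.2.4.2 and 6.1 do not refer to each other, and nothing in the SAP settles either row.

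**Step 2. Show how the any-TEAE rate would respond.** The documents give no AE rates and no rate of CS films, so every input here is an assumption. Let a be the share of subjects with a TEAE other than a disease film, and q the share with a CS film of the qualifying pneumonia recorded as an AE. Taking the two as independent,

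observed rate = 1 − (1 − a)(1 − q).

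*Inflation.* With a = 30% in both arms:
- q = 10%: 1 − 0.70 × 0.90 = 37%
- q = 25%: 1 − 0.70 × 0.75 = 47.5%
- q = 50%: 1 − 0.70 × 0.50 = 65%
- q = 75%: 1 − 0.70 × 0.25 = 82.5%

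*Dilution.* With the same q in both arms, the observed difference is (a₁ − a₀)(1 − q). For a₁ = 50% on drug and a₀ = 20% on placebo, the 30-point difference becomes 27, 22.5, 15 and 7.5 points at the same four values of q.

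*Efficacy carried into safety.* With a = 30% in both arms but q = 25% on drug and 50% on placebo, the observed rates are 47.5% and 65%. The drug appears safer by 17.5 points, all of it from X-ray clearance. With q = 40% and 50%, the rates are 58% and 65%, a gap of 7 points. If the drug slowed clearance, the sign would reverse.

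**Step 3. Scale.** SAP 3.4.1 gives 44 subjects randomized. If the arms are equal (an assumption), that is 22 per arm, and one subject coded one way rather than the other moves an arm's rate by 1/22 = 4.5 points.

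**The case against.** The strongest case against is that the sentence in 5.2.4.2 should not be read alone.

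- The qualifying pneumonia precedes dosing and belongs in medical history. Section 6.5.1 collects events that occur from the first dose and prefers a diagnosis to a sign. The investigator may also grade an expected, resolving film NCS. **This stands in part.** These rules may keep many unchanged films out of the AE data, but none of them says how a persisting film graded CS is handled.
- SAP 3.2.5 plans preferred-term lines and separate tables for treatment-related TEAEs, SAEs, and TEAEs leading to discontinuation or death. Pneumonia terms will be visible there. **This also stands in part.** Those lines do not show how many subjects would still have any TEAE once these films are set aside.
- Randomization and blinding apply the rule to both arms, and no test of TEAE rates is specified. **This is true**, and it rules out a bias built into the design. Equal inflation still dilutes a real difference, and inflation stays equal only if the drug does not affect the films.

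Two stronger readings are tempting. A reader might infer that 6.1 also excludes a residual infiltrate, so that the two sections clash over every abnormal film. They do not: 6.1 speaks of progression, and a stable or improving film is not progression. A reader might also infer that every significant film must be an AE, so that the TEAE rate does count the disease. The text says should, and the documents do not show what sites recorded.

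**Conclusion.** The point holds as a gap plus a narrow contradiction. The gap is that 5.2.4.2 has no condition relative to baseline, so a persisting infiltrate graded CS can be recorded as a TEAE. The contradiction with 6.1 is confined to non-serious worsening films attributed to expected progression. The overall TEAE rate may therefore include the disease under study, and any drug effect on the films would carry into it.

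The size cannot be derived from the documents. It depends on how often films were graded CS and which section each site followed. The percentages under the working show direction and sensitivity under assumed rates and independence; they do not estimate what happened in this trial. This is a minor point, worth acting on because the remedy is cheap.

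**What to change.** **SAP 3.2.5.** Add a TEAE overview that excludes X-ray findings of the qualifying pneumonia that are not SAEs, and place it beside the planned overview of all TEAEs. Sites that recorded such films and sites that left them out are then counted alike. Keeping both versions matters, because the exclusion alone could hide a harmful effect of the drug on the pneumonia. List the excluded events, and identify them before unblinding if the blind still holds.

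**Protocol.** The last subject left on 22-APR-2025 (SAP 2.5), so new wording cannot change the data collected. For any further use of the protocol, reconcile 5.2.4.2 with 6.1 and with the medical-history rule. One way is to tie the X-ray AE rule to the Worsen category already recorded for each later film, and to say how 6.1 applies to it.

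**Cost.** One extra table and a review of AE terms. No new data are needed.

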5.2.4.3. National Institute of Allergy and Infectious Diseases (NIAID) 8-point ordinal scale

The NIAID 8-point ordinal scale used in this study is as follows:

Table 5-3 NIAID 8-point ordinal scale

Score	Description
1	Not hospitalized with no limitation of activities
2	Not hospitalized - limitation of activities or home oxygen, or both
3	Hospitalized with no supplemental oxygen, and no ongoing medical care
4	Hospitalized with no supplemental oxygen, but with ongoing medical care
5	Hospitalized with requirement of supplemental oxygen
6	Hospitalized with need of non-invasive ventilation or high flow oxygen supplementation
7	Hospitalized with invasive mechanical ventilation or extracorporeal membrane oxygenation (ECMO)
8	Death

Disease severity will be evaluated using the National Institute of Allergy and Infectious Diseases (NIAID) 8-point ordinal scale. Higher score indicates deterioration in the clinical status. Disease progression is defined as an increase of score on the NIAID 8-point ordinal scale, such as from Score 1 to Score 3. Health improvement is defined as a reduction of score on the NIAID 8-point ordinal scale, such as from Score 4 to Score 2.

5.2.4.4. RT-PCR

Nasopharyngeal swabs will be used to perform RT-PCR for the following tests:

- Presence of viral RNA (qualitative result: positive or negative)

- Ct values (SARS-CoV-2 Domain only)
- Viral load (SARS-CoV-2 Domain only)

Fully validated RT-PCR tests shall be performed. RT-PCR tests for SARS-CoV-2 Domain will be conducted in the central lab, while testing for the presence of viral RNA for influenza Virus Domain will be performed at each local site lab.

5.2.4.5. Mortality status

Mortality status will be followed up until Day 29 if applicable.

5.2.4.6. Electronic Patient Reported Outcome (ePRO)

An ePRO will be used for subjects to record body temperature from Day 1 to Day 7 or beyond to confirm fever-free (as Section **5.2.5.2 Vital signs**) and the IP intake from Day 1 up to Day 6.

5.2.5. Safety Assessments

5.2.5.1. Physical examination

A complete physical examination will be performed at every visit, including the examination of general appearance, HEENT (head, ears, eyes, nose, throat), neck (including thyroid), lymph nodes, skin, cardiovascular, pulmonary, abdomen, neurological system and musculoskeletal/joints.

A complete physical examination will be performed at each visit. Height and weight will be collected at Visit 1 (Screening Visit) only.

5.2.5.2. Vital signs

The pulse rate, blood pressures in sitting position, respiratory rate, and body temperature will be assessed and recorded in clinic site at each visit. The body temperature assessed at site on Day 1 should be baseline before the start of treatment. Any clinically significant abnormal findings should be record as an adverse event during the study.

After the first dose of CX-4945 or placebo administration on Day 1, subjects will self-measure their body temperature and record it in ePRO four times a day, every 4 to 6 hours.

To confirm fever-free:

After the temperature falls below the fever definition, the subject will continue recording for a minimum of 24 hours.

5.2.5.3. Electrocardiogram

The results of ventricular rate, PR interval, QRS interval, QT interval, and RR interval will be recorded, if available. Corrected QT interval (QTc) will be calculated using Fridericia formula. ECG will be evaluated by the investigators and noted as “Normal”, “Abnormal, non-clinical significant (NCS)” or “Abnormal, clinical significant (CS)” with comments in the CRF/eCRF. The test may be repeated if the original result is questionable.

5.2.5.4. Pulse oxygen saturation

Measuring the amount of oxygen-carrying hemoglobin in the blood relative to the amount of hemoglobin not carrying oxygen will be performed at each visit. Pulse oxygen saturation will be measured using a standard pulse oximeter, oxygen analyzer, or physiologic monitor. Record the FiO₂ accompanying each SpO₂ measurement. Oxygen saturation to fraction of inspired oxygen ratio (SpO₂/FiO₂) will be calculated for statistical analyses.

5.2.5.5. Laboratory test

The following laboratory analyses will be performed. Reference ranges will be used by the investigator to assess the laboratory data for clinical significance and pathological changes.

Hematology

Hemoglobin (Hb), Hematocrit (Hct), Red Blood Cells (RBC), White Blood Cells (WBC), differential of leukocytes, Absolute Neutrophil Count (ANC) and platelets.

Blood Chemistry

- Hepatic function indicators: total bilirubin, alkaline phosphatase (ALP), aspartate aminotransferase (AST), alanine aminotransferase (ALT), total protein, albumin
- Renal function indicators: BUN, Serum creatinine, and eGFR
- Electrolytes: sodium, potassium, chloride, total calcium and bicarbonate

Coagulation

Prothrombin time (PT) and International Normalized Ratio (INR)

Urinalysis

Color, appearance, specific gravity, pH, protein, glucose, occult blood, ketones, leukocyte esterase, nitrite, bilirubin, urobilinogen, and microscopic examination of urine sediment (including red blood cells, white blood cells, epithelial cells, bacteria, casts, and crystals.)

Biomarker evaluations

- Serum cytokine level: [REDACTED]

[REDACTED] Inflammatory biomarkers: [REDACTED]

